16.6. OTHER SAFETY ASSESSMENTS

Inhalation training results on Day 1 pre-dose will be presented in a listing only. In addition, urine pregnancy test results will be listed for women of childbearing potential at Day 1 pre-dose and end of study visits.

Document: Z:\RPL554\AZA40375\Biostatistics\Documentation\SAP\Verona RPL554-DP-201 SAP v2.0 – Part B

Author: [name] / [name]

Version Number: 2.0

Version Date: [08JUL2019]

Template No.: CS_TP_BS016 Revision 5

Reference: CS_WI_BS005

Effective Date: 01Apr2018

Copyright © 2009, 2010, 2012, 2016, 2018 IQVIA. All rights reserved. The contents of this document are confidential and proprietary to IQVIA Holdings Inc. and its subsidiaries. Unauthorized use, disclosure or reproduction is strictly prohibited.

APPENDIX 1. PROGRAMMING CONVENTIONS FOR OUTPUTS

IQVIA OUTPUT CONVENTIONS

Outputs will be presented according to the following:

TABLE AND LISTING OUTPUT CONVENTIONS

General:

- The first row in the body of the table or listing should be blank
- The left-hand column should start in column 1. No indenting or centering of the output should occur.
- Rounding should be done with the SAS function ROUND.
- Numbers in tables should be rounded, not truncated.
- Alphanumeric output should be left aligned.
- Numbers should be decimal point aligned.
- Whole numbers should be right aligned.
- Text values should be left aligned.
- The first letter of a text entry should be capitalized
- Listings of adverse events, concomitant medications, medical histories etc. should be sorted in chronological order, with earliest adverse event, medication or history coming first.
- The study drug should appear first in tables with treatments as columns
- In general, only present totals (across treatment groups) at baseline/randomization, and do not present them post randomization, unless the customer specifically requests it.
- All listing outputs should be sorted (preferably by Treatment, Site Number and Patient Number).
- Exponentiation will be expressed using a superscript with ODS RTF.
- All variables that are output in the CRF (which have data present) should appear in the listings, along with all derived data appearing in the corresponding tables
- The width of the entire output should match the linesize.

Univariate Statistics:

Document: Z:\RPL554\AZA40375\Biostatistics\Documentation\SAP\Verona RPL554-DP-201 SAP v2.0 – Part B

Author: [name] / [name]

Version Number: 2.0

Version Date: [08JUL2019]

Template No.: CS_TP_BS016 Revision 5

Reference: CS_WI_BS005

Effective Date: 01Apr2018

Copyright © 2009, 2010, 2012, 2016, 2018 IQVIA. All rights reserved. The contents of this document are confidential and proprietary to IQVIA Holdings Inc. and its subsidiaries. Unauthorized use, disclosure or reproduction is strictly prohibited.

- Statistics should be presented in the same order across tables (i.e., n, Mean, SD, Minimum, Median, Maximum and equivalently, n, GeoMean, CV, Minimum, Median, Maximum)
- Table statistics should line up under the N part of the (N=XXX) in the table header. All decimal points should line up. If the minimum and maximum are output on 1 line as Minimum, Maximum then the comma should line up with the decimal point.
- If the original data has N decimal places, then the summary statistics should have the following decimal places:
Minimum and maximum: N
Mean, median and CV%: N + 1
SD: N + 2

Frequencies and percentages (n and %):

- Percent values should be reported inside parentheses, with 1 space between the count and the left parenthesis of the percentage. Parentheses should be justified to accept a maximum of 100.0 as a value and padded with blank space if the percent is less than 100.0. An example is given below:

77 (100.0%)

50 (64.9%)

0 (0.0%)

- Percentages will be reported to 1 decimal place, except percentages <100.0% but >99.9% will be presented as '>99.9%' (e.g., 99.99% is presented as >99.9%); and percentages < 0.1% will be presented as '<0.1%' (e.g., 0.08% is presented as <0.1%). Rounding will be applied after the <0.1% and >99.9% rule.

e.g. (<0.1%)

(6.8%)

(>99.9%)

Percentages may be reported to 0 decimal places as appropriate (for example, where the denominator is relatively small).

- Where counts are zero, percentages of 0.0% should appear in the output.

Confidence Intervals:

- As a rule, confidence intervals are output to 1 place more than the raw data, and standard deviations and standard errors to 2 places more than the raw data

Document: Z:\RPL554\AZA40375\Biostatistics\Documentation\SAP\Verona RPL554-DP-201 SAP v2.0 – Part B

Author: [name] / [name]

Version Number: 2.0

Version Date: [08JUL2019]

Template No.: CS_TP_BS016 Revision 5

Reference: CS_WI_BS005

Effective Date: 01Apr2018

Copyright © 2009, 2010, 2012, 2016, 2018 IQVIA. All rights reserved. The contents of this document are confidential and proprietary to IQVIA Holdings Inc. and its subsidiaries. Unauthorized use, disclosure or reproduction is strictly prohibited.

- Confidence intervals should be justified so that parentheses displayed on consecutive lines of a table “line up”.
- Boundary values of confidence intervals should be separated by a comma.
- Boundary values should be padded as necessary to accept negative values and to allow alignment of the decimal place.
- An example is given below:
(-0.12, -0.10)
(9.54, 12.91)

P-values:

- P-values should be reported to 4 decimal places, except values <1.000 but >0.999 will be presented as ‘>0.999’ (e.g., 0.9998 is presented as >0.999); and values <0.001 will be presented as ‘<0.001’ (e.g., 0.0009 is presented as <0.001). Rounding will be applied after the <0.001 and >0.999 rule

Ratios:

- Ratios should be reported to 1 more decimal place than the original data.

Spacing:

- There must be a minimum of 1 blank space between columns (preferably 2)

Denominators:

- If a different count other than the population count is used for a denominator (within the table) to calculate percentages, there should be a row in the table that identifies that number “n”.
- Alternatively, a footnote should be included in each table with percentages to indicate the denominator for percentages.

Missing values

- A “0” should be used to indicate a zero frequency.
- A blank will be used to indicate missing data in an end-of-text table or patient listing.

Document: Z:\RPL554\AZA40375\Biostatistics\Documentation\SAP\Verona RPL554-DP-201 SAP v2.0 – Part B

Author: [name] / [name]

Version Number: 2.0

Version Date: [08JUL2019]

Template No.: CS_TP_BS016 Revision 5

Reference: CS_WI_BS005

Effective Date: 01Apr2018

Copyright © 2009, 2010, 2012, 2016, 2018 IQVIA. All rights reserved. The contents of this document are confidential and proprietary to IQVIA Holdings Inc. and its subsidiaries. Unauthorized use, disclosure or reproduction is strictly prohibited.

FIGURE OUTPUT CONVENTIONS

- Figures should be provided in RTF files generated by SAS.
- Should contain the title or footer.
- The image should be clear and of high quality when viewed in the Word document, and when printed.
- In general, boxes around the figures should be used.

DATES & TIMES

Depending on data available, dates and times will take the form DDMMYY YYYY THH:MM:SS.

SPELLING FORMAT

English US.

PRESENTATION OF TREATMENT GROUPS

For outputs, treatment groups will be represented as follows and in this order:

Treatment Group	For Tables, Graphs and Listings
RPL554 150 µg double blind	RPL554 150µg
RPL554 500 µg double blind	RPL554 500µg
RPL554 1500 µg double blind	RPL554 1500µg
RPL554 3000 µg double blind	RPL554 3000µg
Placebo	Placebo
Non-randomized (where applicable)	Non-randomized

PRESENTATION OF TREATMENT SEQUENCES

For outputs, treatment sequences will be represented as follows and in that order:

Treatment Group	For Tables, Graphs and Listings
RPL554 150 mcg db/RPL554 1500 mcg db/ RPL554 3000 mcg db /RPL554 500 mcg db/Placebo	Seq 1

Document: Z:\RPL554\AZA40375\Biostatistics\Documentation\SAP\Verona RPL554-DP-201 SAP v2.0 – Part B

Author: [name] / [name]

Version Number: 2.0

Version Date: [08JUL2019]

Template No.: CS_TP_BS016 Revision 5

Reference: CS_WI_BS005

Effective Date: 01Apr2018

Copyright © 2009, 2010, 2012, 2016, 2018 IQVIA. All rights reserved. The contents of this document are confidential and proprietary to IQVIA Holdings Inc. and its subsidiaries. Unauthorized use, disclosure or reproduction is strictly prohibited.

Treatment Group	For Tables, Graphs and Listings
RPL554 150 mcg db/ RPL554 3000 mcg db /Placebo/RPL554 500 mcg db/RPL554 1500 mcg db	Seq 2
RPL554 500 mcg db/ RPL554 3000 mcg db /RPL554 150 mcg db/Placebo/RPL554 1500 mcg db	Seq 3
RPL554 500 mcg db/RPL554 150 mcg db/RPL554 1500 mcg db/Placebo/ RPL554 3000 mcg db	Seq 4
RPL554 1500 mcg db/RPL554 500 mcg db/Placebo/RPL554 3000 mcg db/RPL554 150 mcg db	Seq 5
RPL554 1500 mcg db/Placebo/RPL554 150 mcg db/ RPL554 3000 mcg db /RPL554 500 mcg db	Seq 6
RPL554 3000 mcg db/RPL554 1500 mcg db/RPL554 500 mcg db/RPL554 150 mcg db/Placebo	Seq 7
RPL554 3000 mcg db/Placebo/RPL554 1500 mcg db/ RPL554 150 mcg db /RPL554 500 mcg db	Seq 8
Placebo/RPL554 150 mcg db/RPL554 500 mcg db/RPL554 1500 mcg db/RPL554 3000 mcg db	Seq 9
Placebo/RPL554 500 mcg db/RPL554 3000 mcg db/RPL554 1500 mcg db/RPL554 150 mcg db	Seq 10
Undefined sequence, not mentioned above	Undefined
Non-randomized (where applicable)	Non-randomized

db = double blind

PRESENTATION OF VISITS

For outputs, visits will be represented as follows and in that order, considering there will be 5 treatment periods (1 to 5):

Long Name (default)	Short Name
Screening	Scr
Day 1	Day 1
Day 7	Day 7
End of Study	EOS
Overall (where applicable)	Overall

Document: Z:\RPL554\AZA40375\Biostatistics\Documentation\SAP\Verona RPL554-DP-201 SAP v2.0 – Part B

Author: [name] / [name]

Version Number: 2.0

Version Date: [08JUL2019]

Template No.: CS_TP_BS016 Revision 5

Reference: CS_WI_BS005

Effective Date: 01Apr2018

Copyright © 2009, 2010, 2012, 2016, 2018 IQVIA. All rights reserved. The contents of this document are confidential and proprietary to IQVIA Holdings Inc. and its subsidiaries. Unauthorized use, disclosure or reproduction is strictly prohibited.

LISTINGS

All listings will be ordered by the following (unless otherwise indicated in the template):
Randomized treatment group (or treatment received if it's a safety output), first by active dose [by ascending dose group] and then placebo.
Center-patient ID,
Date (where applicable),
For listings where non-randomized patients are included, these will appear in a category after the randomized treatment groups labeled 'Non-randomized'.

APPENDIX 2. PARTIAL DATE CONVENTIONS

Imputed dates will NOT be presented in the listings.

ALGORITHM FOR TREATMENT EMERGENCE OF ADVERSE EVENTS

START DATE	STOP DATE	ACTION
Known	Known, Partial or Missing	If start date < study med start date, then not TEAE If start date >= study med start date, then TEAE
Partial, but known components show that it cannot be on or after study med start date	Known, Partial or Missing	Not TEAE
Partial, could be on or after study med start date	Known	If stop date < study med start date, then not TEAE If stop date >= study med start date, then TEAE
	Partial	Impute stop date as latest possible date (i.e. last day of month if day unknown or 31st December if day and month are

Document: Z:\RPL554\AZA40375\Biostatistics\Documentation\SAP\Verona RPL554-DP-201 SAP v2.0 – Part B

Author: [name] / [name]

Version Number: 2.0

Version Date: [08JUL2019]

Template No.: CS_TP_BS016 Revision 5

Reference: CS_WI_BS005

Effective Date: 01Apr2018

Copyright © 2009, 2010, 2012, 2016, 2018 IQVIA. All rights reserved. The contents of this document are confidential and proprietary to IQVIA Holdings Inc. and its subsidiaries. Unauthorized use, disclosure or reproduction is strictly prohibited.

START DATE	STOP DATE	ACTION
		unknown), then: If stop date < study med start date, then not TEAE If stop date >= study med start date, then TEAE
	Missing	Assumed TEAE
Missing	Known	If stop date < study med start date, then not TEAE If stop date >= study med start date, then TEAE
	Partial	Impute stop date as latest possible date (i.e. last day of month if day unknown or 31st December if day and month are unknown), then: If stop date < study med start date, then not TEAE If stop date >= study med start date, then TEAE
	Missing	Assumed TEAE

ALGORITHM FOR PRIOR / CONCOMITANT MEDICATIONS

START DATE	STOP DATE	ACTION
Known	Known	If stop date < study med start date, assign as prior If stop date >= study med start date and start date <= end of treatment, assign as concomitant If stop date >= study med start date and start date > end of treatment, assign as post study
	Partial	Impute stop date as latest possible date (i.e. last day of month if day unknown or 31st December if day and month are unknown), then: If stop date < study med start date, assign as prior If stop date >= study med start date and start date <= end of treatment, assign as concomitant

Document: Z:\RPL554\AZA40375\Biostatistics\Documentation\SAP\Verona RPL554-DP-201 SAP v2.0 – Part B

Author: [name] / [name]

Version Number: 2.0

Version Date: [08JUL2019]

Template No.: CS_TP_BS016 Revision 5

Reference: CS_WI_BS005

Effective Date: 01Apr2018

Copyright © 2009, 2010, 2012, 2016, 2018 IQVIA. All rights reserved. The contents of this document are confidential and proprietary to IQVIA Holdings Inc. and its subsidiaries. Unauthorized use, disclosure or reproduction is strictly prohibited.

START DATE	STOP DATE	ACTION
	Missing	If stop date is missing could never be assumed a prior medication If start date <= end of treatment, assign as concomitant
Partial	Known	Impute start date as earliest possible date (i.e. first day of month if day unknown or 1st January if day and month are unknown), then: If stop date < study med start date, assign as prior If stop date >= study med start date and start date <= end of treatment, assign as concomitant
	Partial	Impute start date as earliest possible date (i.e. first day of month if day unknown or 1st January if day and month are unknown) and impute stop date as latest possible date (i.e. last day of month if day unknown or 31st December if day and month are unknown), then: If stop date < study med start date, assign as prior If stop date >= study med start date and start date <= end of treatment, assign as concomitant
	Missing	Impute start date as earliest possible date (i.e. first day of month if day unknown or 1st January if day and month are unknown), then: If stop date is missing could never be assumed a prior medication If start date <= end of treatment, assign as concomitant
Missing	Known	If stop date < study med start date, assign as prior If stop date >= study med start date, assign as concomitant
	Partial	Impute stop date as latest possible date (i.e. last day of month if day unknown or 31st December if day and month are unknown), then: If stop date < study med start date, assign as prior If stop date >= study med start date, assign as concomitant
	Missing	Assign as concomitant

 Document: Z:\RPL554\AZA40375\Biostatistics\Documentation\SAP\Verona RPL554-DP-201 SAP v2.0 – Part B

Author: [name] / [name]

Version Number: 2.0

Version Date: [08JUL2019]

Template No.: CS_TP_BS016 Revision 5

Reference: CS_WI_BS005

Effective Date: 01Apr2018

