7.4.1.2 Recording and Assessing Adverse Events

All adverse events, whether reported spontaneously by the patient, in response to open questioning on treatment days or observed by the Investigator or his/her staff, will be recorded from informed consent until the End of Study Visit. The start and stop time will be recorded and adverse events will be assessed by the Investigator for the following:

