16.1. ADVERSE EVENTS

Adverse Events (AEs) will be coded by MedDRA dictionary using the version specified in the data management plan.

Treatment emergent adverse events (TEAEs) are defined as AEs that started or worsened in severity on or after the single dose of study medication, based on the investigator assessment of severity. TEAEs will be assigned to treatment groups based on actual treatment received.

See [Appendix 2](#) for handling of partial dates for AEs. In the case where it is not possible to define an AE as treatment emergent or not, the AE will be classified by the worst case; i.e. treatment emergent.

An overall summary of number of patients within each of the categories described in the sub-section below, will be provided as specified in the templates.

Listings will include TEAEs and Non-TEAEs.

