16.1. ADVERSE EVENTS

Adverse Events (AEs) will be coded by MedDRA dictionary using the version specified in the data management plan.

Treatment emergent adverse events (TEAEs) are defined as AEs that started or worsened in severity on or after the first dose of study medication, based on the investigator assessment of severity. TEAEs will be assigned to treatment groups based on actual treatment received. TEAEs, like medications, may be assigned to multiple treatment groups due to the cross-over design of the study. This will depend on the occurrence date and duration of each TEAE.

See [Appendix 2](#) for handling of partial dates for AEs. In the case where it is not possible to define an AE as treatment emergent or not, the AE will be classified by the worst case; i.e. treatment emergent.

An overall summary of number of patients within each of the categories described in the sub-section below, will be provided as specified in the templates.

Listings will include TEAEs and Non-TEAEs.

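### For known or certainly pre-dose start dates, Appendix 2 of both SAPs ignores worsening and same-day start times, so it conflicts with the TEAE definition in Section 16.1

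*SAP*

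**What the plan says.** The Part B SAP, Section 16.1, defines TEAEs as "AEs that started or worsened in severity on or after the first dose of study medication". The Part A SAP, Section 16.1, uses the same definition for its one dose: "AEs that started or worsened in severity on or after the single dose of study medication". Both sections send the reader to Appendix 2 for partial dates and apply a worst-case default when emergence cannot be determined.

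Appendix 2 of each SAP goes further than partial dates. For a fully known start date it rules "If start date < study med start date, then not TEAE" and "If start date >= study med start date, then TEAE". A start date described as "Partial, but known components show that it cannot be on or after study med start date" is also classed as not treatment emergent, whatever the stop date. If the start date is missing, or is partial and could fall on or after dosing, the stop date decides ("If stop date >= study med start date, then TEAE"), and a missing stop date means the event is assumed to be a TEAE. No row mentions severity or clock time.

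Protocol Section 7.4.1.2 collects adverse events from consent onward and says of each event: "The start and stop time will be recorded". Protocol Section 5.10 has the exact time of each in-clinic dose entered in the eCRF.

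**The concern.** The definition and the algorithm meant to implement it disagree, and the program will follow the algorithm. The disagreement runs in two directions.

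- **Omission.** An event that began before dosing and became more severe afterwards is a TEAE by definition but not by algorithm. Serious TEAEs, TEAEs leading to discontinuation and TEAEs leading to death (Sections 16.1.2 to 16.1.4 of both SAPs) are all summarised from the TEAE set. An event that worsened and became serious after dosing could therefore be missing from those tables and appear only in listings.
- **Addition.** An event that began on the dosing day before the dose is not a TEAE by definition but is one by algorithm. Dosing is preceded that morning by two spirometry sessions, an ECG and adverse event questioning, and in Part B also by safety blood tests.

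Safety is a secondary objective in both parts, and the protocol synopsis says Part A safety data informed the choice of Part B doses. With six patients per Part A arm, one misclassified patient changes an incidence by 1/6, about 17 percentage points. That is the arithmetic of one hypothetical patient, not an estimate of what happened.

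**Working it through.** The plan gives no figure to reproduce, so the check is of classification logic.

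**Step 1. Rows affected.** The Part B table has 8 start/stop rows. Two (start known; start partial but certainly pre-dose) ignore the stop date, and 8 − 2 = 6 use the stop date or default to TEAE. The Part A table writes the same logic in 12 rows, of which 6 use the stop date or the default. The conflict lies in the 2 Part B rows and the other 6 Part A rows.

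**Step 2. Definition against algorithm.** Ten constructed events were classified both ways. Day 0 is the dosing day, and the dose is assumed to be at 09:00, inside the 7 to 11 am window of Protocol Section 5.3.2.

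| Constructed event | Section 16.1 | Appendix 2 |
|---|---|---|
| Known start day −3, worsens day +2 | TEAE | **not TEAE** |
| Partial start, certainly pre-dose, worsens day +2 | TEAE | **not TEAE** |
| Known start 07:30 on day 0, no worsening | not TEAE | **TEAE** |
| Ambiguous partial start, true onset day −3, no worsening, stops day +5 | not TEAE | **TEAE** |
| Ambiguous partial start, true onset day −3, worsens day +2, stops day +5 | TEAE | TEAE |
| Missing start and stop, true onset day −3, worsens day +2 | TEAE | TEAE |
| Known start 07:30 on day 0, worsens 10:00 | TEAE | TEAE |
| Known start 10:00 on day 0 | TEAE | TEAE |
| Known start day −3, no worsening | not TEAE | not TEAE |
| Missing start, stops day −1 | not TEAE | not TEAE |

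Four of the ten differ. The fourth is the stated worst-case default at work, because the recorded data cannot settle the matter; it is not an error. The first three are real conflicts: two omissions and one addition. The default does not cover them, since in each the recorded data settle the question or the table gives a definite answer.

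**Step 3. Length of the same-day window.** With dosing between 07:00 and 11:00, the part of the dosing date that precedes the dose is 7/24 = 29% to 11/24 = 46%. Recorded start and dose times can separate the two parts.

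**Step 4. Visits concerned.** Part B emergence is set against the first dose. Part B SAP Sections 6.1 and 12 place the start of Part B study medication at Treatment Period 1, Day 1. With approximately 36 patients, the visits concerned are 36 (Part A) + up to 36 (Part B, Period 1) = 72.

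**The case against.** Most of the case on the other side limits the size of the point, and much of it stands.

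- A reader might infer that Appendix 2 decides on start date alone. It does not. Where the start date is ambiguous or missing, worsened events that continue past dosing are kept.
- A reader might count every Day 1 visit: 36 + 36 × 5 = 216. The documents do not support this. A pre-dose event on Day 1 of Periods 2 to 5 falls after the first Part B dose, so Section 16.1 itself makes it a TEAE. Those 36 × 4 = 144 visits raise a different question, namely which treatment the event is assigned to.
- A reader might conclude that worsened events are certainly lost. Protocol Section 7.4.1.1 includes worsening in its definition of an adverse event. If sites open a new record with its own start date, Appendix 2 already captures the worsening. The documents neither state nor exclude that practice. Listings include non-TEAEs, so nothing disappears from the report.
- A reader might infer a known bias, or a dilution of dose differences. One rule under-counts and the other over-counts, so the net direction is unknown. Over-counting same-day events is conservative, and a background added equally to all arms leaves absolute differences nearly unchanged. Adverse event summaries are descriptive.
- The remark in Protocol Section 1.2 that most dizziness occurred during spirometry or dosing does not separate pre-dose from post-dose. Part B Day 1 has two pre-dose and nine post-dose spirometry times.

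One defence fails. Section 16.1 cites Appendix 2 only for partial dates, but the table has explicit rows for known start dates and a programmer would apply them.

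**Conclusion.** The point holds within limits. In both SAPs, a known or certainly pre-dose start date is classed as not treatment emergent with no check for worsening, and an onset on the dosing date is classed as treatment emergent regardless of its recorded time. Each rule contradicts Section 16.1.

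It bears on onsets before or on the day of the Part A dose and the first Part B dose, about 72 dosing visits. The number of events cannot be computed because the documents give no adverse event counts or rates. The under-count assumes that worsening is not entered as a new record. The visit count assumes about 36 patients in each part, and that emergence in Part B runs from Period 1, Day 1. No efficacy or pharmacokinetic endpoint or test is affected. The correction should be made because these tables are the main safety summaries and the data needed are already collected.

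**What to change.** In Appendix 2 of both SAPs:

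1. Add a row: start before dosing, but severity increased on or after dosing, is a TEAE from the time of worsening. Alternatively, state that worsening is entered as a new adverse event record with its own start date and time, and put the same instruction in the eCRF completion notes.
2. Where a start time is available, compare the start date and time with the dose date and time. Treat a missing start time on the dosing day as a TEAE.

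Part A has already been locked, unblinded and analysed, so apply the rule there as a documented check or re-run in the study report.

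The cost is a few lines of SAP text and code and, if needed, an eCRF note. Event times and in-clinic dose times are already collected. If worsening was not recorded as a separate entry or with a date, it may not be recoverable for past events, and the report should say so.
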